### 7.3.3. Exploratory Patient Reported Outcomes (PROs) Analyses

#### 7.3.3.1. Endpoints

- Percentage of patients meeting a responder threshold of  $\geq 0.09$  points improvement from baseline (randomisation) for the ASUI total score at month 6
- Change from baseline (randomisation) in ASUI total score at month 6
- Percentage of patients meeting a responder threshold of  $\geq 4$  points improvement (decrease) from baseline (randomisation) for the SGRQ total score at month 6
- Change from baseline (randomisation) in SRGQ total score at month 6
- Change from baseline (screening) in PAM total score at month 6
- Change from baseline (screening) in MARS-A total score at month 6
- Change from baseline (screening) in BMQ – General Benefit score at month 6
- Change from baseline (screening) in BMQ – General Harm score at month 6
- Change from baseline (screening) in BMQ – General Overuse score at month 6
- Change from baseline (screening) in BMQ – Specific Necessity score at month 6
- Change from baseline (screening) in BMQ – Specific Concern score at month 6

### 7.3.3.2. Summary Measure

The PRO summary measures to determine treatment arm effect are:

- An adjusted odds ratio on percentage of patients meeting a responder threshold of  $\geq 0.09$  points improvement from baseline for the ASUI total score at Month 6, along with a 95% confidence interval and p-value for the percentage, analysed using a logistic regression model.
- The difference in LS means of the change from baseline in ASUI total score at month 6, along with a 95% confidence interval and p-value for the difference, analysed using an MMRM model.
- An adjusted odds ratio on percentage of patients meeting a responder threshold of  $\geq 4$  points improvement (decrease) from baseline for the SGRQ total score at Month 6, along with a 95% confidence interval and p-value for the percentage, analysed using a logistic regression model.
- The difference in LS means of the change from baseline in SGRQ total score at month 6, along with a 95% confidence interval and p-value for the difference, analysed using an MMRM model.
- Mean change from baseline (screening) in PAM-13 total score at month 6.
- Mean change from baseline (screening) in MARS-A total score at month 6
- Mean change from baseline (screening) in BMQ – General Benefit score at month 6
- Mean change from baseline (screening) in BMQ – General Harm score at month 6
- Mean change from baseline (screening) in BMQ – General Overuse score at month 6
- Mean change from baseline (screening) in BMQ – Specific Necessity score at month 6
- Mean change from baseline (screening) in BMQ – Specific Concern score at month 6

### 7.3.3.3. Population of Interest

The PRO exploratory summaries and analysis will be based on the “Intent-to-Treat” population.

### 7.3.3.4. Strategy for Intercurrent (Post-Randomisation) Events

Intercurrent events for the ASUI and SGRQ outcomes were identified as:

- Early discontinuation of ELLIPTA
- Early discontinuation of the APP
- Early discontinuation of ELLIPTA sensor
- Early discontinuation of MDI sensor
- Early withdrawal from study
- Use of MDI rescue medication
- Use of prohibited medications
- Change of dose of ELLIPTA

The “Treatment policy” strategy will be applied to handle the “Early discontinuation of ELLIPTA sensor”, “Early discontinuation of the APP”, “Early discontinuation of MDI sensor”, “Use of MDI rescue medication”, “Use of prohibited medications” and “change of dose of ELLIPTA” for all PRO exploratory endpoints. The strategy implies direct use of PRO data irrespective of the occurrence of these intercurrent events.

**7.3.3.4.1. *Percentage of patients meeting a responder threshold of  $\geq 0.09$  points improvement from baseline (randomisation) for the ASUI total score at Month 6 (Visit 10)***

The “Composite” strategy will be used for the “Early discontinuation of ELLIPTA” and ‘Early discontinuation of study’ intercurrent events. In the occurrence of these intercurrent events, the effect to be estimated will be the effect on the outcome of achieving an improvement from baseline of  $\geq 0.09$  in ASUI total score at month 6 and remaining on ELLIPTA (off-ELLIPTA treatment data is not collected). Participants who do not meet the improvement threshold, have missing values for their ASUI total score at month 6, or discontinue using ELLIPTA or the study will be classified as non-responders in all planned analyses for this endpoint.

The “Treatment policy” strategy will be used to handle discontinuation of the APP/sensor. This means direct assessment of ASUI total score at month 6 against the responder criteria, irrespective of CIS discontinuation status.

**7.3.3.4.2. *Change from baseline (randomisation) in ASUI total score at month 6 (Visit 10)***

The “treatment policy” strategy will be applied to all handle all the intercurrent events listed in 7.4.3.4. In other words, all observed data before early discontinuation of the study respective of treatment status (on-treatment) or CIS discontinuation status will be included in the analysis. No missing data will be imputed, missing data will be considered MAR. Therefore, the primary treatment effect to be estimated will be the mean change from baseline in ASUI total score at month 6 and remaining on the study.

**7.3.3.4.3. *Percentage of patients meeting a responder threshold of  $\geq 4$  points improvement (decrease) from baseline (randomisation) for the SGRQ total score at month 6 (Visit 10)***

The “Composite” strategy will be used for the “Early discontinuation of ELLIPTA” and ‘Early discontinuation of study’ intercurrent events. In the occurrence of these intercurrent events, the effect to be estimated will be the effect on the outcome of achieving an improvement from baseline of  $\geq 4$  in SGRQ total score at month 6 and remaining on ELLIPTA (off-ELLIPTA treatment data is not collected). Participants who do not meet the improvement threshold, have missing values for their SGRQ total score at month 6, or discontinue using ELLIPTA or the study will be classified as non-responders in all planned analyses for this endpoint.

The “Treatment policy” strategy will be used to handle discontinuation of the APP/sensor. This means direct assessment of SGRQ total score at month 6 against the responder criteria, irrespective of CIS discontinuation status.

#### **7.3.3.4.4. *Change from baseline (Randomisation) in SGRQ total score at Month 6 (Visit 10)***

The “treatment policy” strategy will be applied to all handle all the intercurrent events listed in 7.4.3.4. In other words, all observed data before early discontinuation of the study respective of treatment status (on-treatment) or CIS discontinuation status will be included in the analysis. No missing data will be imputed, missing data will be considered MAR. Therefore, the primary treatment effect to be estimated will be the mean change from baseline in SGRQ total score at month 6 and remaining on the study.

#### **7.3.3.4.5. *Change from baseline (Screening) in PAM-13, MARS-A, and BMQ total score at Month 6 (Visit 10)***

The mean change from baseline in PAM-13, MARS-A and all scales for the BMQ questionnaires at month 6 will be summarised using descriptive statistics (n, mean, SD, median, min, max) for each treatment arm. The “treatment policy” strategy will be applied to all handle all the intercurrent events listed in 7.4.3.4. In other words, all observed data before early discontinuation of the study respective of treatment status (on-treatment) or CIS discontinuation status will be included in the analysis. No missing data will be imputed, missing data will be considered MAR. Therefore, the primary treatment arm effect to be estimated will be the mean change from baseline in total score at month 6 and remaining on the study.

No formal statistical analyses will be performed for these endpoints.

#### **7.3.3.5. *Statistical Analyses / Methodology Specification***

Details of the planned displays will be provided in Section 10.8, Appendix 8: List of Data Displays and will be based on GSK data standards and statistical principles.

Unless otherwise specified, endpoints / variables defined in Section 7.3.3.1, Endpoints, will be summarised using descriptive statistics, graphically presented (where appropriate) and listed.

#### **7.3.3.5.1. *Increase from Baseline of $\geq 0.09$ in ASUI total score at Month 6 (Visit 10)***

Endpoint / Variables
Percentage of patients meeting a responder threshold of $\geq 0.09$ points improvement from baseline for the ASUI total score at Month 6 (Visit 10)
Model Specification
This endpoint will be analysed using a logistic regression model. Only the month 6 (visit 10) data will be included in the model. Month 1 (visit 5) data will not be implemented since by this timepoint participants may not have reverted to steady medicating behaviour

Terms in the model:

- Dependent variable: ASUI responder/non-responder score (binary score)
- Covariates:
  - Categorical: randomised treatment arm, gender and country
  - Continuous: baseline ASUI total score and age.

Patients who have a missing ASUI total score at month 6 (visit 10) (i.e. no ASUI data on-treatment) will be classified as non-responders at that visit. This rule will apply to all above analyses.

Computation of confidence intervals for the odds ratios is based in the individual Wald tests.

#### Model Checking & Diagnostics

If the likelihood maximisation algorithm fails to converge due to complete or quasi-complete separation of the data then Firth's penalized likelihood ([Firth](#), 1993) will be implemented by use of the FIRTH option on the MODEL statement in PROC LOGISTIC.

The fit of the logistic regression model will be assessed by examining the ROC curve and other diagnostic plots.

#### Model Results Presentation

The number and percentage of participants with a response within each randomised treatment arm will be presented by visit, together with the adjusted odds ratio comparing CIS Arms 1, 2, 3, 4 with Arm 5, associated 95% CIs and p-values.

### 7.3.3.5.2. Change from baseline (Randomisation) in ASUI total score at Month 6 (Visit 10)

Endpoint / Variables
Mean change from baseline in ASUI total score at Month 6 (Visit 10)
Model Specification
This endpoint will be analysed using a mixed model repeated measures (MMRM) model utilising the REML estimation approach and the default unstructured covariance matrix structure. Whilst missing data are not implicitly imputed in this analysis, there is an underlying assumption that the data are MAR. All non-missing data for a participant will be used within the analysis and, via modelling of the within-participant correlation structure, the derived treatment differences will be adjusted to take into account missing data.
Model Checking & Diagnostics

 
Dependent Variable: change from baseline in ASUI total score at month 6
 
Covariates: 
 
Fixed categorical: randomised treatment arm, visit (month 1 and 6), gender and country.
 
Fixed continuous: baseline ASUI total score and age
 
Interaction terms: randomised treatment arm-by-visit, baseline ASUI total score-by-visit
 
Random effect: participant
 
 
 

Model Checking & Diagnostics

 
If this model fails to converge, alternative correlation structures may be considered
 
Appropriate graphs will be reviewed as part of the model checking process to ensure that distributional assumptions hold. These will include a normal probability plot of the residuals and a plot of the residuals versus the fitted values (checking the normality assumption and constant variance assumption of the model, respectively).
 
Interactions with treatment will be explored for other model covariates and tests for interactions will be at the 2-sided 10% significance level. Any significant interactions that are found will be thoroughly investigated and where necessary, extra outputs will be produced.
 

Model Results Presentation
Adjusted mean change from baseline values for each treatment arm will be presented with their associated standard errors. The estimated treatment difference along with corresponding standard error, 95% confidence interval (CI) and p-value will be presented for the treatment comparisons at month 6 (Visit 10).

#### 7.3.3.5.3. Increase from Baseline of $\geq 4$ in SGRQ total score at Month 6 (Visit 10)

Endpoint / Variables
Percentage of patients meeting a responder threshold of $\geq 4$ points improvement from baseline for the SGRQ total score at month 6
Model Specification
This endpoint will be analysed using a logistic regression model. Only the month 6 (visit 10) data will be included in the model. Month 1 (visit 5) data will not be implemented since by this timepoint participants may not have reverted to steady medicating behaviour
Terms in the model: 
 
Dependent variable: SGRQ responder/non-responder score (binary score)
 
Covariates: 
 
Categorical: randomised treatment arm, gender and country
 
Continuous: baseline SGRQ total score and age.
 
 
 
 Patients who have a missing SGRQ total score at month 6 (visit 10) (i.e. no SGRQ data on-treatment) will be classified as non-responders at that visit. This rule will apply to all above analyses.
Computation of confidence intervals for the odds ratios is based in the individual Wald tests.
Model Checking & Diagnostics
If the likelihood maximisation algorithm fails to converge due to complete or quasi-complete separation of the data then Firth's penalized likelihood ( Firth , 1993) will be implemented by use of the FIRTH option on the MODEL statement in PROC LOGISTIC.
The fit of the logistic regression model will be assessed by examining the ROC curve and other diagnostic plots.
Model Results Presentation
The number and percentage of participants with a response within each randomised treatment arm will be presented by visit, together with the adjusted odds ratio comparing CIS Arms 1, 2, 3, 4 with Arm 5, associated 95% CIs and p-values.

#### 7.3.3.5.4. Change from baseline (Randomisation) in SGRQ total score at Month 6 (Visit 10)

Endpoint / Variables
Mean change from baseline in SGRQ total score at Month 6 (Visit 10)
Model Specification
This endpoint will be analysed using a mixed model repeated measures (MMRM) model utilising the REML estimation approach and the default unstructured covariance matrix structure. Whilst missing data are not implicitly imputed in this analysis, there is an underlying assumption that the data are MAR. All non-missing data for a participant will be used within the analysis and, via modelling of the within-participant correlation

structure, the derived treatment differences will be adjusted to take into account missing data.

Terms fitted in the model will include:

- Dependent Variable: change from baseline in SGRQ total score at month 6
- Covariates:
  - Fixed categorical: randomised treatment arm, visit (month 1 and 6), gender and country.
  - Fixed continuous: baseline SGRQ total score and age
  - Interaction terms: randomised treatment arm-by-visit, baseline SGRQ total score-by-visit
  - Random effect: participant

#### Model Checking & Diagnostics

- If this model fails to converge, alternative correlation structures may be considered
- Appropriate graphs will be reviewed as part of the model checking process to ensure that distributional assumptions hold. These will include a normal probability plot of the residuals and a plot of the residuals versus the fitted values (checking the normality assumption and constant variance assumption of the model, respectively).
- Interactions with treatment will be explored for other model covariates and tests for interactions will be at the 2-sided 10% significance level. Any significant interactions that are found will be thoroughly investigated and where necessary, extra outputs will be produced.

#### Model Results Presentation

Adjusted mean change from baseline values for each treatment arm will be presented with their associated standard errors. The estimated treatment difference along with corresponding standard error, 95% confidence interval (CI) and p-value will be presented for the treatment comparisons at month 6 (Visit 10).

### 7.3.4. Exploratory Fractionated Exhaled Nitric Oxide (FeNO) and Peak Expiratory Flow (PEF) Analyses

#### 7.3.4.1. Endpoints

- FeNO at Screening (Visit 1), Randomisation (Visit 2,3 or 4), Month 1 (Visit 5) and Month 6 (Visit 10).
- Change from baseline (randomisation) in FeNO measured at Month 1 (Visit 5) and Month 6 (Visit 10)
- PEF at Screening (Visit 1), Randomisation (Visit 2,3 or 4), Month 1 (Visit 5) and Month 6 (Visit 10).
- Change from baseline (randomisation) in PEF measured at Month 1 (Visit 5) and Month 6 (Visit 10)

#### 7.3.4.2. Summary Measures

The FeNO and PEF summary measures are:

- Summary statistics (n, mean, SD, median, min, max) for each treatment arm of screening (Visit 1), Randomisation (Visit 2,3 or 4), Month 1 (Visit 5) and Month 6 (Visit 10) and changes from baseline (screening) at month 1 (visit 5) and month 6 (visit 10)

### 7.3.4.3. Population of Interest

The FeNO and PEF exploratory summaries will be based on the Intent-to-Treat population.

### 7.3.4.4. Strategy for Intercurrent (Post-Randomisation) Events

Intercurrent events for the FeNO and PEF outcomes were identified as:

- Early discontinuation of ELLIPTA
- Early discontinuation of the APP
- Early discontinuation of ELLIPTA sensor
- Early discontinuation of MDI sensor
- Early withdrawal from study
- Use of MDI rescue medication
- Use of prohibited medications
- Change of dose of ELLIPTA

The “Treatment policy” strategy will be applied to handle all intercurrent event for the FeNO and PEF exploratory endpoints. The strategy implies direct use of FeNO and PEF data irrespective of the occurrence of these intercurrent events.

### 7.3.4.5. Statistical Analyses / Methodology Specification

Details of the planned displays will be provided in Section 10.8, [Appendix 8](#): List of Data Displays and will be based on GSK data standards and statistical principles.

Unless otherwise specified, endpoints / variables defined in Section 7.3.4.1 Endpoints will be summarised using descriptive statistics, graphically presented (where appropriate) and listed. No formal statistical analyses will be performed for these endpoints.

Endpoint

 
• FeNO at Screening (Visit 1), Randomisation (Visit 2,3 or 4), Month 1 (Visit 5) and Month 6 (Visit 10)
 
• Change from baseline (randomisation) in FeNO measured at Month 1 (Visit 5) and Month 6 (Visit 10)
 
• PEF at Screening (Visit 1), Randomisation (Visit 2,3 or 4), Month 1 (Visit 5) and Month 6 (Visit 10)
 
• Change from baseline (randomisation) in PEF measured at Month 1 (Visit 5) and Month 6 (Visit 10)
 

Summary

All endpoints to be summarised using descriptive statistics (n, mean, SD, median, min, max) for each randomised treatment arm.
 
To explore the impact of maintenance adherence levels on FeNO and PEF, the following displays will be presented,
 
 
• Summary statistics (n, mean, SD, median, min, max) of change from baseline at Month 6 (Visit 10) in FeNO per quartile of the observed primary endpoint measure, percentage of ELLIPTA doses taken (daily adherence) between the beginning of Month 4 and the end of Month 6 as determined by the
 

maintenance sensor

- Summary statistics (n, mean, SD, median, min, max) of change from baseline at Month 6 (Visit 10) in PEF per quartile of the observed primary endpoint measure, percentage of ELLIPTA doses taken (daily adherence) between the beginning of Month 4 and the end of Month 6 as determined by the maintenance sensor
- Note: the quartiles of a ranked adherence data values are four subsets whose boundaries are the three quartile points (25th, 50th and 75th percentiles)
- A scatter plot of the change from baseline at Month 6 (Visit 10) in FeNO by observed primary endpoint measure will be presented. This will be repeated for change from baseline at Month 6 (Visit 10) in PEF.

### **7.3.5. Qualitative data from exit interviews**

Analysis of the qualitative data from exit interviews will be analyzed following a separate qualitative analysis plan and presented in a separate Clinical Study Report (CSR).

## 8. SAFETY ANALYSES

Safety analyses will be based on the ITT Population and will include all study data (run-in, on and post-treatment), unless otherwise specified.

Safety endpoints will include:

- Incidence and type of serious adverse events
- Incidence and type of adverse drug reactions (ADR)
- Incidence and type of non-serious adverse events leading to study withdrawal

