### 8.1. Adverse Events Analyses

SAEs, AEs leading to withdrawal and non-serious ADRs will be collected.

The incidence of any given adverse event (SAE, ADR or non-serious AEs leading to withdrawal) for each treatment group is defined as the proportion of participants in that group who have experienced at least one such adverse event during the study period.

Adverse event (SAE or ADR) summaries including the summary of adverse drug reactions (ADRs), Serious (SAEs) and non-serious adverse events leading to withdrawal of study will be based on GSK Core Data Standards. The details of the planned displays are provided in Section [10.8 Appendix 8: List of Data Displays](#).

Adverse events will be coded using the Medical Dictionary for Regulatory Activities (MedDRA) coding dictionary. The version of MedDRA used in reporting will be noted in a footnote of the AE overview table.

For the standard on-treatment and post-treatment AE tables, the number and percentage of participants with all AEs (regardless of causality) will be summarized for each treatment group by system organ class (SOC) and preferred term (PT). The ordering of the SOCs and the PTs within the SOCs will both be in descending order of total incidence. A SOC will not be presented when the overall incidence for any AE within the particular system is zero. If the total incidence for any two or more AEs is equal, the events will be presented in alphabetical order.

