### 10.3.1.3. Treatment Emergent Flag for Adverse Events

Study Phase	Definition
Run-in-Treatment*	(AE Start Date $\geq$ Screening Visit date) and (AE Start Date $<$ Randomisation Date)
On-Treatment	(AE Start Date $\geq$ Randomisation Date) and (AE Start Date $\leq$ Last Treatment Stop Date)+1
Post-Treatment	AE Start Date $>$ Treatment Stop Date + 1
Onset Time Since First Dose (days)*	
Time Since First Dose will be derived as follows:
 
 
• If Randomisation Date or AE Onset Date are missing => missing
 
• If Randomisation Date <math>></math> AE Onset Date then => AE Onset Date – Randomisation Date
 
• If Randomisation Date <math>\leq</math> AE Onset Date then => AE Onset Date – Randomisation Date + 1
 

\*For participants who enter the run-in treatment phase but do not get randomised, use the last run-in date instead of randomisation date for the “Run-in-Treatment” phase and “Onset Time Since First Dose (days)” as the participants would not have a randomisation date.

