### 10.4.2. Reporting Standards

General		

 
The current GSK Integrated Data Standards Library (IDSL) will be applied for reporting, unless otherwise stated (IDSL Standards Location: https://spope.gsk.com/sites/IDSLLibrary/SitePages/Home.aspx):           
 
4.03 to 4.23: General Principles
 
5.01 to 5.08: Principles Related to Data Listings
 
6.01 to 6.11: Principles Related to Summary Tables
 
7.01 to 7.13: Principles Related to Graphics
 
 
 
		
All data displays (Tables, Figures & Listings) will use the term "Subject" which reflects CDISC and GSK Data Display Standards terminology		
Formats		

 
GSK IDSL Statistical Principles (5.03 & 6.06.3) for decimal places (DP's) will be adopted for reporting of data based on the raw data collected, unless otherwise stated.
 
Numeric data will be reported at the precision collected on the eCRF.
 
The reported precision from non eCRF sources will follow the IDSL statistical principles but may be adjusted to a clinically interpretable number of DP's.
 
All data will be reported according to the treatment the participant was randomised to unless otherwise stated.
 
Numeric data will be reported (in listings) at the precision collected in the eCRF or recorded in the raw dataset if from non-eCRF sources.
 
		
Specification of Number of Decimal Places for Descriptive Statistics		
Label	Description	Number of decimal places (dp) more than raw data
N	Number of participants in the treatment group	Always present to 0 dp
n	Number of participants with non-missing values	Always present to 0 dp
Mean	Arithmetic Mean	1 dp

SD	Standard Deviation	2 dp		
Median	Median	1 dp		
Min.	Minimum	0 dp		
Max.	Maximum	0 dp		
Specification of Number of Decimal Places for Statistical Analysis				
Label	Description	Number of decimal places (dp) more than raw data		
LS Mean	Adjusted mean for the treatment group	1 dp		
LS Mean Change	Adjusted mean change from baseline for the treatment group	1 dp		
Std Err	Standard error	2 dp		
Difference	Treatment difference	1 dp		
Odds Ratio	Treatment odds ratio	Always present to 2 dp		
Relative Risk	Treatment relative risk	Always present to 2 dp		

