#### 10.8.8. Safety Tables

Safety: Tables					
No.	Population	IDSL / Example Shell	Title	Programming Notes	Deliverable [Priority]
Adverse Events (AEs)					
3.1.	ITT	SAFE_T1	Overview of On-Treatment and Post-Treatment Non-Serious AEs leading to Withdrawal, Non-Serious ADRs and SAEs	Include total column	SAC [2] DRY RUN [1]
3.2.	ITT	SAFE_T1	Overview of Run-In Treatment Non-Serious AEs leading to Withdrawal, Non-Serious ADRs and SAEs	Include total column	SAC [2] DRY RUN [1]

Safety: Tables					
No.	Population	IDSL / Example Shell	Title	Programming Notes	Deliverable [Priority]
3.3.	Not in ITT	SAFE_T1	Overview of Run-In Treatment Non-Serious AEs leading to Withdrawal, Non-Serious ADRs and SAEs for Subjects not in ITT	Total column only	SAC [2] DRY RUN [1]
3.4.	ITT	IDSL_AE15	Summary of Common (>=1%) Non-serious Adverse Events by System Organ Class and Preferred Term (Number of Subjects and Occurrences)	Include total column. Do not apply rounding.  Footnote: Non-serious Adverse Events includes non-serious ADRs and non-serious AEs leading to withdrawal  Disclosure table.	SAC [2] DRY RUN [1]
3.5.	ITT	IDSL_AE15	Summary of Common (>=1%) Run-In Treatment Non-Serious Adverse Events by System Organ Class and Preferred Term (Number of Subjects and Occurrences)	Include total column only. Do not apply rounding.  Footnote: Non-serious Adverse Events includes non-serious ADRs and non-serious AEs leading to withdrawal  Disclosure table.	SAC [2] DRY RUN [1]
3.6.	Not in ITT	IDSL_AE15	Summary of Common (>=1%) Run-In Treatment Non-Serious Adverse Events by System Organ Class and Preferred Term (Number of Subjects and Occurrences) for Subjects not in ITT	Include total column only. Do not apply rounding.  Footnote: Non-serious Adverse Events includes non-serious ADRs and non-serious	SAC [2] DRY RUN [1]

Safety: Tables					
No.	Population	IDSL / Example Shell	Title	Programming Notes	Deliverable [Priority]
				AEs leading to withdrawal Disclosure table.	
Adverse Drug Reactions (ADRs)					
3.7.	ITT	IDSL_AE1	Summary of On-Treatment Adverse Drug Reactions	Include total column. All ADRs (Non-serious and Serious)	SAC [2] DRY RUN [1]
3.8.	ITT	IDSL_AE1	Summary of Post-Treatment Adverse Drug Reactions	Include total column. All ADRs (Non-serious and Serious)	SAC [2] DRY RUN [1]
3.9.	ITT	IDSL_AE1	Summary of On-Treatment Serious Adverse Drug Reactions	Include total column	SAC [2] DRY RUN [1]

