3.10.	ITT	IDSL_AE1	Summary of Post-Treatment Serious Adverse Drug Reactions	Include total column	SAC [2] DRY RUN [1]
3.11.	ITT	IDSL_AE1	Summary of On-Treatment Non-Serious Adverse Drug Reactions	Include total column	SAC [2] DRY RUN [1]
3.12.	ITT	IDSL_AE1	Summary of Post-Treatment Non-Serious Adverse Drug Reactions	Include total column	SAC [2] DRY RUN [1]

Safety: Tables					
No.	Population	IDSL / Example Shell	Title	Programming Notes	Deliverable [Priority]
Serious Adverse Events (SAEs)					
3.13.	ITT	IDSL_AE16	Summary of Serious Adverse Events by System Organ Class and Preferred Term (Number of Subjects and Occurrences)	Include total column	SAC [2] DRY RUN [1]
3.14.	ITT	IDSL_AE16	Summary of Run-In Treatment Serious Adverse Events by System Organ Class and Preferred Term (Number of Subjects and Occurrences)	Include total column	SAC [2] DRY RUN [1]
3.15.	Not in ITT	IDSL_AE16	Summary of Run-In Treatment Serious Adverse Events by System Organ Class and Preferred Term (Number of Subjects and Occurrences) for Subjects not in ITT	Include total column	SAC [2] DRY RUN [1]
3.16.	ITT	IDSL_AE1	Summary of On-Treatment Serious Adverse Events	Include total column	SAC [2] DRY RUN [1]
3.17.	ITT	IDSL_AE1	Summary of Post-Treatment Serious Adverse Events	Include total column	SAC [2] DRY RUN [1]
Adverse Events leading to Withdrawal					
3.18.	ITT	IDSL_AE1	Summary of All On-treatment or Post-Treatment Adverse Events Leading to Permanent Discontinuation of Study Drug or Withdrawal from Study	Footnote: All Adverse Events includes ADRs, SAEs and Non-serious AEs leading to withdrawal  Include total column	SAC [2] DRY RUN [1]

Safety: Tables					
No.	Population	IDSL / Example Shell	Title	Programming Notes	Deliverable [Priority]
3.19.	ITT	IDSL_AE1	Summary of All On-treatment or Post-Treatment Serious Adverse Events Leading to Permanent Discontinuation of Study Drug or Withdrawal from Study	Include total column	SAC [2] DRY RUN [1]
3.20.	ITT	IDSL_AE1	Summary of On-treatment or Post-Treatment Non-Serious Adverse Events Leading to Permanent Discontinuation of Study Drug or Withdrawal from Study	Include total column	SAC [2] DRY RUN [1]
3.21.	ITT	IDSL_AE1	Summary of On-treatment or Post-Treatment Adverse Drug Reactions Leading to Permanent Discontinuation of Study Drug or Withdrawal from Study	Include total column	SAC [2] DRY RUN [1]
Adverse Events of Special Interest					

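### Four by-arm safety tables with no stated phase would, under the SAP Section 8 default, show run-in events under an arm assigned only later

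*SAP*

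**What the plan says.** SAP Section 8 sets the default: "Safety analyses will be based on the ITT Population and will include all study data (run-in, on and post-treatment), unless otherwise specified". Section 8.1 defines incidence for each treatment group as "the proportion of participants in that group who have experienced at least one such adverse event during the study period", without limiting the phase. Section 10.4.2 fixes the column an event appears in: "All data will be reported according to the treatment the participant was randomised to unless otherwise stated".

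Section 10.3.1.3 flags each adverse event as run-in (start on or after the screening visit and before the randomisation date), on-treatment or post-treatment. Section 10.5.1 says that displays will name the phases they include, where applicable.

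Protocol 5.1 (Flexible Run-in) says that neither participant nor HCP receives sensor data during run-in. The Schedule of Activities collects non-serious adverse drug reactions and non-serious events leading to withdrawal from the start of run-in, and SAEs from screening, so run-in events will be in the database.

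**The concern.** The arms differ only in which sensor data are fed back and to whom, and feedback begins at randomisation. An event that started before then cannot be caused by the arm. A table that lists it under that arm answers no question about the arm.

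The affected displays are prominent. Table 3.4 is marked as a disclosure table, 3.13 is the SAE summary with occurrences, and 3.28 and 3.29 are the plain-language displays. Adding a component with the same expected size to every arm raises all the percentages, moves ratios between arms towards one and adds variance to differences. It also makes tables disagree without telling the reader why.

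**Working it through.** The plan gives no figure to reproduce here. The check is which tables inherit the default, followed by arithmetic for scale.

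**1. Phase named in each safety table (SAP 10.8.8, Tables 3.1 to 3.29)**

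| Phase in title | Tables |
|---|---|
| On- plus post-treatment | 3.1 |
| Run-in, ITT | 3.2, 3.5, 3.14 |
| Run-in, not in ITT | 3.3, 3.6, 3.15 |
| On-treatment | 3.7, 3.9, 3.11, 3.16, 3.22 to 3.27 |
| Post-treatment | 3.8, 3.10, 3.12, 3.17 |
| On- or post-treatment | 3.18 to 3.21 |
| None | 3.4, 3.13, 3.28, 3.29 |

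Two adjacent titles show the contrast. Table 3.4 is "Summary of Common (>=1%) Non-serious Adverse Events by System Organ Class and Preferred Term (Number of Subjects and Occurrences"; Table 3.5 is "Summary of Common (>=1%) Run-In Treatment Non-Serious Adverse Events by System Organ Class and Preferred Term (Number of Subjects and Occurrences". The second overrides the default and the first does not. The notes for 3.4, 3.13, 3.28 and 3.29 ask for a total column, which implies a total beside the arm columns. Table 3.5, by contrast, asks for the total column only. Nothing in the notes of the four tables restricts the phase, so the Section 8 default governs them.

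**2. Reconciliation with Table 3.1.** The shell for 3.1 has by-arm rows for any SAE and any non-serious AE, under an on- plus post-treatment title. A participant whose only SAE fell in run-in is absent from 3.1 but present in 3.13 under the later arm. The same can happen in 3.4, less directly because it lists only common terms. That participant's event also appears in 3.2 and 3.14. A common non-serious run-in event also appears in 3.2 and 3.5, where 3.5 does not split by arm.

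**3. Share of the window.** Inputs: run-in of 1, 2 or 3 months (protocol 5.1), taken as 28, 56 or 84 days; treatment to Day 168 and follow-up at Day 175 (Schedule of Activities). For a completer, the share is r / (r + 168 + 7).

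- r = 28: 28/203 = 13.8%
- r = 56: 56/231 = 24.2%
- r = 84: 84/259 = 32.4%

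A participant with ACT below 20 at the first monthly visit is randomised then, so the last two figures apply only to those who needed a second or third month. The documents do not say how many that will be.

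**4. Effect on the proportion with at least one event.** At a constant rate λ per person-year, the proportion is 1 − exp(−λT/365.25), with T in days. The rates are assumptions, not from the documents.

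| λ | T = 175 | T = 203 | T = 231 | T = 259 |
|---|---|---|---|---|
| 0.02 | 0.95% | 1.11% | 1.26% | 1.41% |
| 0.05 | 2.37% | 2.74% | 3.11% | 3.48% |
| 0.10 | 4.68% | 5.41% | 6.13% | 6.85% |

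The relative increase is about 16% for a one-month run-in and 46 to 48% for a three-month run-in, the same in expectation in every arm.

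**5. The 1% cut-off in 3.4, 3.28 and 3.29.** With 432/5 ≈ 86 per arm, one participant is 1/86 = 1.16%. If the cut-off applies per arm, a single run-in event could bring a term into the table. If it applies to the total, 0.01 × 432 = 4.32, so five participants are needed. The SAP does not say which.

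**The case against.** The strongest reply is that this is missing labelling rather than a chosen analysis. Table 3.4 is followed by run-in counterparts for ITT (3.5) and non-ITT (3.6), and 3.13 by 3.14 and 3.15. That layout suggests 3.4 and 3.13 were meant to be post-randomisation. All four tables use sponsor standard shells that are not reproduced, and those might carry a treatment-emergent restriction. This is plausible, but it is inference. The written default says the opposite, and a programmer following the SAP would include run-in events.

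Three further replies stand and limit the point:

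- By-arm tables with post-randomisation windows already exist (3.1, 3.7 to 3.12, 3.16 to 3.27), and safety comparisons are descriptive (SAP 2.4). No post-randomisation SAE or ADR summary is lost.
- Participants take Relvar/Breo from entry to run-in (SAP 10.3.1), so run-in events matter for drug safety, particularly for the drug-related tables 3.28 and 3.29. That justifies reporting them, but not under an arm that had not been assigned.
- The constant rate is doubtful. ITT participants are those who got through run-in, and anyone withdrawn for an event during run-in is not randomised. The withdrawal component of 3.4 and 3.29 can therefore contribute few run-in events.

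**Conclusion.** The point holds for four tables. Followed as written, Section 8 places pre-randomisation events in the by-arm columns of 3.4, 3.13, 3.28 and 3.29. The consequences are inflated by-arm incidence, diluted and noisier differences between arms, and unexplained disagreement with Table 3.1. The 14% share for a one-month run-in (24% or 32% for longer ones) gives scale only. It rests on a constant event rate, completion of follow-up and 28-day months, and it is a share of time rather than a forecast of the share of events.

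A reader might infer more than the documents support:

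- That the safety comparison is biased between arms. Run-in precedes randomisation, so its events are balanced in expectation.
- That events are counted twice. The repetition is across tables; no single table counts an event twice.
- That the four tables conflict with all of 3.7 to 3.12 as on-treatment displays. Tables 3.8, 3.10 and 3.12 are post-treatment, and tables with different stated windows are expected to differ. The fault is that these four state no window.

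No efficacy result is touched. The change should still be made before reporting, because disclosure and plain-language figures are involved.

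**What to change.** - Restrict the by-arm columns of Tables 3.4, 3.13, 3.28 and 3.29 to events flagged on-treatment or post-treatment under SAP 10.3.1.3, and use the same window for the total beside them so that it equals the sum of the arms.
- State that phase in the four titles.
- Add the exception to the default in Section 8.
- Keep run-in events for ITT participants in 3.2, 3.5 and 3.14, where they remain available for the safety assessment of Relvar/Breo.

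The cost is four titles, one sentence in Section 8 and one filter on a flag already defined. No new data are needed.
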